7.0 Drug Administration

The responsibility for treatment of patients rests with the individual investigator.

7.1 Drug Preparation and Administration

7.1.1 Drug Preparation

The appropriate number of vials of CPX-351 (cytarabine:daunorubicin) Liposome Injection should be removed from the refrigerator prior to reconstitution. Reconstitute with 19 mL of water for injection using a 20 mL syringe. Do not heat CPX-351 (cytarabine:daunorubicin) Liposome Injection. After reconstitution, invert vials gently 3-4 times and let rest for 15 minutes prior to withdrawing drug for dilution. CPX-351 (cytarabine:daunorubicin) Liposome Injection should be diluted in approximately 500 mL of saline injection or dextrose injection.

The IV bags and infusion sets must be non-DEHP. Aseptic technique must be strictly observed throughout the handling of CPX-351 (cytarabine:daunorubicin) Liposome Injection, since no bacteriostatic agent or preservative is present. The infusion of CPX-351 (cytarabine:daunorubicin) Liposome Injection must be started within 4 hours of dilution. Vials are for single use. Unused material should be recorded as such and discarded according to institutional policies. Procedures for proper handling and disposal of anticancer drugs should be implemented.

7.1.2 Drug Administration

The infusion of CPX-351 (cytarabine:daunorubicin) Liposome Injection will be performed through a central venous catheter, using an infusion pump to ensure that the drug is infused over the specified time period. Non-DEHP containing administration sets should be used. **Do not use an in-line filter.** CPX-351 should never be given by the intramuscular or subcutaneous route. Administer CPX-351 over approximately 90 minutes via an infusion pump. Flush the line to ensure administration of the full dose.

The dosage (total units and u/m^2), start/stop time of the infusion, total volume infused, must be documented in the patient's chart.

7.2 Drug Accountability

The study pharmacist or designee must maintain records of the delivery of CPX-351 to the study site, the inventory at the site, the use by each patient, and the disposition of unused product. These records should include dates, quantities, lot numbers, expiration dates and patient identifications. The institution should maintain records that document adequately that patients were provided the doses specified by the protocol and reconcile all investigational product received from the manufacturer. Records of storage conditions (temperature logs) must be kept for the entire period that CPX-351 is maintained at the institution. Unused or expired drug will be disposed per MDACC policy.

7.3 Dose Reductions and Delays

Induction doses are not reduced. Consolidation doses are 65 units/m² on days 1 and 3. In instances with prolonged myelosuppression or other medical conditions where the investigator feels further dose reduction might be required, 50 units/m² on days 1 and 3 may be used after discussion with PI and sponsor and documentation of rationale.

Patients with evidence of delayed recovery from cytopenias or acute toxicities following induction or consolidation (>56 days) may have consolidation doses delayed by up to 2 weeks to permit recovery. Any doses missed or delayed due to toxicity may be administered as soon as the patient has recovered from the toxicity. Toxicities will be graded using the CTCAE Version 4.0 (See APPENDIX 5: Common Terminology Criteria for Adverse Events V4.0 (CTCAE)).

7.4 Concomitant Therapy

7.4.1 Premedication

Nausea and vomiting:

Patients may receive prophylaxis or therapy for nausea and/or vomiting according to institutional standards.

Hypersensitivity/Infusion-related reactions:

Patients will not be routinely pre-medicated for hypersensitivity or infusion-related reactions initially during the first infusion of the first treatment course. If the patient develops a hypersensitivity reaction then he/she should be pre-medicated at all subsequent infusions.

7.4.2 *Suggested guidelines for management of hypersensitivity reactions:*

Mild symptoms (e.g., mild flushing, rash, pruritus):

Stop infusion and supervise at bedside with monitoring of vital signs
Reinitiate infusion slowly (halving the rate of infusion) +/- premedication

Moderate symptoms (e.g. moderate rash, flushing, mild dyspnea, chest discomfort):

Stop infusion and give IV diphenhydramine, 20-25 mg (or equivalent) and IV dexamethasone 10 mg.

Do not reinitiate infusion. Subsequent doses should be administered with premedication (e.g., IV diphenhydramine, 20-25 mg (or equivalent) and IV dexamethasone 10 mg) and may be given at the same dose and rate.

Severe/life-threatening symptoms (e.g. hypotension requiring vasopressor therapy, angioedema, respiratory distress requiring bronchodilation therapy, generalized urticaria):

Stop infusion. Administer IV diphenhydramine and dexamethasone as indicated above. Add epinephrine (adrenaline) or bronchodilators if indicated. Do not reinitiate infusion. Do not retreat. Report this event as a serious adverse event.

If hypersensitivity or infusion-related reactions become a clinically relevant toxicity, then premedication for hypersensitivity reactions will be instituted with drugs, doses and schedule according to each investigator's preference. Additionally, a decision may be made to prolong the infusion time to two hours or more.

7.4.3 Permitted therapy

Patients may receive ongoing supportive and palliative care (e.g. pain control) as clinically indicated throughout the study.

Infection Prophylaxis: Prophylactic use of anti-infectives is highly recommended during the period of profound neutropenia until ANC returns to 500/ μ L or greater. The choice of anti-infectives will be according to institutional protocol. Use of anti-infective agents as prophylaxis and treatment must be documented on the case report forms.

Growth Factor support: The use of growth factors will be according to institutional protocol and/or according to ASCO criteria.(14) Use of growth factors must be documented on the case report forms.

Transfusion support: The use of transfusion support (RBCs and platelets) will be according to institutional protocol. Use of transfusion support must be documented on the case report forms.

7.4.4 Therapy that is not permitted

Other anti-cancer treatment and other investigational therapy(ies) are not permitted during the Treatment Phase. In the event of persistent disease or relapse the patient may receive other anti-leukemic therapies. Administration of isolated doses of intrathecal chemotherapy is allowed.

7.5 Duration of Protocol Treatment

Patients may continue on study provided they have not met the criteria for discontinuation of therapy (See Section 5.2). The table below summarizes the expected duration of the Treatment Phase. Patients may receive up to two induction courses followed by consolidation courses. After the Treatment Phase, patients are followed until death.

8.0 Assessment of Efficacy

8.1 Evaluable for Efficacy

All patients receiving one or more doses of study therapy are evaluable for efficacy.

8.2 Overall Survival

All enrolled patients are assessed for overall survival. Overall survival is measured from the date of registration to death from any cause, patients not known to have died at last follow-up are censored on the date they were last known to be alive.

8.3 Event-free Survival

All enrolled patients are assessed for Event-free survival. Event-free survival is defined as the time from study registration to the date of induction treatment failure (persistent disease), relapse from CR or CRi, initiation of non-protocol chemotherapy (e.g. salvage therapy), or death from any cause, whichever comes first. Patients transferred to transplant will be censored for Event-free Survival at the start of conditioning therapy. Patients alive and not known to have any of these events are censored on the date they were last examined.

8.4 Response Assessment Criteria

During the Treatment Phase patients will be assessed for response according to the following criteria(15):

Complete remission (CR) ¹	Bone marrow blasts <5%; absence of blasts with Auer rods; absence of extramedullary disease; absolute neutrophil count $>1.0 \times 10^9/L$ (1000/ μ L); platelet count $>100 \times 10^9/L$ (100,000/ μ L).
CR with incomplete recovery (CRI) ²	All CR criteria except for residual neutropenia ($<1.0 \times 10^9/L$ [1000/ μ L]) and/or thrombocytopenia ($<100 \times 10^9/L$ [100,000/ μ L])
Treatment failure	
Persistent Disease (PD)	Failure to achieve CR or CRI; only includes patients surviving ≥ 7 days following completion of initial treatment, with evidence of persistent leukemia by blood and/or bone marrow examination
Death in aplasia	Deaths occurring ≥ 7 days following completion of initial treatment while cytopenic; with an aplastic or hypoplastic bone marrow obtained within 7 days of death, without evidence of persistent leukemia
Death from indeterminate cause	Deaths occurring before completion of therapy, or <7 days following its completion; or deaths occurring ≥ 7 days following completion of initial therapy with no blasts in the blood, but no bone marrow examination available
Relapse ³	Bone marrow blasts $\geq 5\%$ (confirmed); or confirmed, sustained reappearance of blasts in the blood after achievement of a CR or CRI, not considered due to recovery from chemotherapy; or development of extramedullary disease

¹All criteria need to be fulfilled; marrow evaluation should be based on a count of 200 nucleated cells in an aspirate with spicules; if ambiguous, consider repeat exam after 5 to 7 days; flow cytometric evaluation may help to distinguish between persistent leukemia and regenerating normal marrow; a marrow biopsy should be performed in cases of dry tap, or if no spicules are obtained; no minimum duration of response required.

²Some patients may not achieve complete hematologic recovery prior to initiation of consolidation. CRI usually cannot be declared earlier than Day 42 to allow for adequate time for documentation of peripheral blood recovery. Consolidation usually begins no earlier than 42 days after the last induction course.

³In cases with low blast percentages (5-10%), a repeat marrow should be performed to confirm relapse. Appearance of new dysplastic changes should be closely monitored for emerging relapse. In a patient who has been recently treated, dysplasia or a transient increase in blasts may reflect a chemotherapy effect and recovery of hematopoiesis.

The response of patients with no post-baseline bone marrow assessment is entered as not done.

8.4.1 Timing of response assessment

In general, the patient's response to induction therapy is made on the first day when all criteria for CR or treatment failure are met. The bone marrow assessment and the

peripheral counts are not required to be performed on the same day but recovery of counts (including absence of peripheral blasts) must be performed within 14 days of the bone marrow assessment.

8.4.2 Best Response

Patients who complete the induction(s) with a response of CRi may be upgraded to a CR during or after consolidation if the patient's peripheral blood counts meet the criteria for CR after declaration of a CRi. To upgrade a response to CR both peripheral blood and bone marrow assessment must be obtained within a 14 day period and all criteria for CR must be met.

8.5 Remission Duration

Only patients achieving CR or CRi are assessed for remission duration (relapse-free survival). Remission duration is measured from the date of achievement of a remission (CR/CRi) until the date of relapse or death from any cause; patients not known to have relapsed or died at last follow-up are censored on the date they were last examined.

8.6 Morphologic Leukemia-free State

All randomized patients that have at least one evaluable post-randomization bone marrow assessment performed on or after Day 14 after the last induction are assessed for morphologic leukemia-free state. Morphologic leukemia-free state is defined as bone marrow blasts <5% AND absence of Auer rods and/or extramedullary disease.

9.0 Assessment of Safety

9.1 Evaluable for Safety

All patients who have received at least one dose will be considered evaluable for safety.

9.2 Adverse Events

9.2.1 Definition of an Adverse Event

An adverse event is any untoward medical occurrence in a patient or clinical investigation subject administered with a pharmaceutical product and which does not necessarily have to have a causal relationship with this treatment. An adverse event can therefore be any unfavorable and unintended sign (including an abnormal laboratory finding, for example), symptom, or disease temporally associated with the use of a medicinal product, whether or not considered related to the medicinal product. This includes worsening of a pre-existing condition or increase in frequency of a pre-existing condition. An adverse event is considered serious if it meets any of the serious criteria listed in Section 9.2.2. To ensure no confusion or misunderstanding of the difference between the terms "serious" and "severe", which are not synonymous, the following clarification is provided:

The term "severe" is often used to describe the intensity (severity) of a specific event (as in mild, moderate, or severe myocardial infarction); the event itself, however, may be of relatively minor medical significance (such as severe headache). This is not the same as

“serious”, which is based on patient/event outcome or action criteria usually associated with events that pose a threat to a patient’s life or functioning. Seriousness (not severity) serves as a guide for defining regulatory reporting obligations.

Adverse events are to be recorded in the case report form from the start of the infusion on Day 1 until 30 days after the last dose of study drug, with the exception of serious adverse events. (See Section 9.2.2). Leukemia Department Guidelines for AE recording will be used.

The Investigator or physician designee is responsible for verifying and providing source documentation for all adverse events and assigning the attribution for each event for all subjects enrolled on the trial.

Adverse events and protocol specific data will be entered into CORe/PDMS. CORe/PDMS will be used as the electronic case report form for this protocol.

Adverse drug reactions (ADRs) are all noxious and unintended responses to a medicinal product related to any dose that a causal relationship between the medicinal product and an adverse event is at least a reasonable possibility, i.e., the relationship cannot be ruled out. An unexpected ADR is any adverse reaction not identified in nature or intensity in the current Investigator’s Brochure.

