4.0 Study Design

One cycle equals 28 days.

This study is an open-label, two-arm or possibly 3-arm, phase II trial. CPX-351 is administered as approximately a 90-minute infusion on days 1, 3, and 5 with one study arm receiving 50 units/m² and the other receiving 75 units/m². Both the 50 and the 75 unit/m² dose levels are considered to have acceptable safety based on observations from a pair of randomized Phase II studies conducted in adult patients, where the observed 60-day mortality results in patients considered fit for intensive chemotherapy and with no prior history of stem cell transplant, was observed to be reduced compared to control.

Patients with newly diagnosed AML who are predicted to be at high risk (30-50%) for induction mortality (death by day 60) are eligible. Every patient entered must have at least one AML-related factor (adverse cytogenetics, secondary AML, MDR phenotype, etc.) that contributes to elevated risk of induction mortality. Patients may or may not have patient-related factors (poor performance status, co-morbidities, poor organ function, etc.) that also contribute to elevated risk of induction mortality. 30 patients will be randomized with a 1:1 ratio to the two dose arms with 15 patients per arm to assess for safety and efficacy. If safety is demonstrated for both of the sub-MTD dose levels, and escalation is deemed feasible above 75 units/m², a cohort of 15 patients will be studied at 100 units/m², the MTD dose level. The latter dose (i.e., 100 units/m²) was found safe and an additional 25 patients will be enrolled at this dose (for a total of 40 evaluable patients) to define efficacy at this standard dose.

At the end of the study a single dose level will be confirmed to have acceptable safety if the observed rate of dose limiting toxicity (DLT) is <5 DLT/15 patients.<33%). Dose limiting toxicity is defined as induction mortality (death occurring during the first 60 days from start of study therapy), grade 3 or 4 non-hematologic toxicity, or dose limiting

hematologic toxicity at least possibly related to the study drug occurring during the first 60 days from the start of study therapy (i.e., during the first cycle of therapy).

For non-hematologic toxicity the following are counted as dose limiting toxicities only under the conditions noted:

- Liver toxicity: Grade 4, related to the study drug, not resolving to grade 2 within 7 days.

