4.8 Patient Follow-up

Follow-up for CR duration, EFS and safety (if applicable) terminates at the time of relapse, start of salvage or non-protocol treatment for leukemia (for persistent disease or transplant conditioning chemotherapy).

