Adverse Events/Toxicity	CTCAE v.4 assessment	Beginning at the start of the first infusion, continually assess during Treatment Period and record and report any new serious adverse events (up to 30 days after completion of Treatment Period)
Concomitant Medications		Continually assess during Treatment Period
Correlative studies (optional)*	Immune effects	Before induction and at start of 1 st and 2 nd consolidation
Correlative studies (optional)*	BNP, Troponin I, high-sensitivity troponin (I or T)	Before the start of each cycle, and approximately 24 hrs from end of infusion on day 1 and day 5 of each cycle, and approximately on day 14 (± 4 days) of each cycle, end of treatment.
Correlative studies (optional)*	Pharmacodynamics	Pre-dose and 24-hrs (± 4 hrs) after first dose.

* Failure to collect samples for optional studies will not constitute a protocol deviation.

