6.3 Early Termination or End of Treatment

Any patient that completes or discontinues treatment must have the following evaluations performed within 30 days after termination and prior to the initiation of any salvage therapy, if not performed within the last 30 days:

Procedure	Evaluation	Timing
Physical exam	Objective review of body systems ECOG Performance Status	Within 30 days after discontinuation
Vital signs	Heart rate Blood pressure Temperature Respiratory rate	Within 30 days after discontinuation
Hematology	Hemoglobin White Blood Count Platelets Differential Count (may be omitted if WBC $\leq 0.5 \times 10^9/L$)	Within 30 days after discontinuation
Biochemistry	BUN Creatinine Electrolytes (Sodium, Potassium, Chloride) Bilirubin AST or ALT	Within 30 days after discontinuation
Diagnostic Imaging	Echocardiography/MUGA	Within 30 days after discontinuation if a study has not been performed since last treatment but before the initiation of any non-protocol treatment
ECG		Within 30 days after discontinuation
Copper levels	Serum Copper	Within 30 days after discontinuation if a study has not been performed since last treatment
Adverse Events/Toxicity	CTCAE v.4 assessment	Assess Adverse events that were ongoing at the time of discontinuation and record and report any new serious adverse events (up to 30 days after discontinuation)
Correlative studies (optional)*	BNP, Troponin I, high-sensitivity troponin (I or T)	Within 30 days after discontinuation

* Failure to collect samples for optional studies will not constitute a protocol deviation.

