6.4 Evaluation during Long-term Follow-up

The following evaluations are completed during the follow-up phase (i.e., after completion of all therapy to continue for one year except for survival and relapse status which will continue until death and relapse, respectively):

Procedure	Evaluation	Timing
Patient status report	Survival status	Until death
	Relapse status New anti-leukemic therapies	Monthly until relapse or the initiation of new therapy
Hematology	Hemoglobin Hematocrit Red Blood Count White Blood Count Platelets Differential Count (may be omitted if WBC $\leq 0.5 \times 10^9/L$)	Every 2-3 months for one year until relapse or the initiation of new therapy, then as clinically indicated.
Bone Marrow Aspiration and/or Biopsy	Morphology	Every 3-4 months. For patients in CR, consider performing if peripheral blood counts fall below 1000/ μL for ANC or 100,000/ μL for platelets for >1 month with no obvious explanation for the drop or at any time there is suspicion of relapse; for patients in CRI perform if counts fall significantly below peak recovery. If the peripheral blood counts in a patient with a CRI recover to CR levels ($\geq 1000/\mu L$ for ANC or $\geq 100,000/\mu L$ for platelets), consider performing a bone marrow evaluation to confirm full CR. Following the first year of follow up, aspirations will be done as clinically indicated; record relapse information, including any bone marrow evaluations. Not required following the initiation of new therapy and or relapse.
Diagnostic Imaging	Echocardiography or MUGA	Perform every 3-4 months if last Treatment Phase LVEF was reduced >10% from baseline and is less than 50%. Continue assessments until LVEF returns to baseline or until 1 year from start of therapy.
Biochemistry	BUN Creatinine Bilirubin AST or ALT	Every 2-3 months for one year until relapse or the initiation of new therapy, then as clinically indicated.
Copper levels	Serum Copper	Perform monthly only if elevated copper (>20% above ULN) present at EOT. Perform every 1 month until abnormality returns to within 20% of ULN, or until 1 year, or the initiation of new therapy, or relapse (whichever is earliest)

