- Unless otherwise noted, the electronic SAE application (eSAE) will be utilized for safety reporting to the IND Office and MDACC IRB.
- Serious adverse events will be captured from the time of the first protocol-specific intervention, until 30 days after the last dose of drug, unless the participant withdraws consent. Serious adverse events must be followed until clinical recovery is complete and laboratory tests have returned to baseline, progression of the event has stabilized, or there has been acceptable resolution of the event.
- Additionally, any serious adverse events that occur after the 30 day time period that are related to the study treatment must be reported to the IND Office. This may include the development of a secondary malignancy.

Reporting to FDA:

- Serious adverse events will be forwarded to FDA by the IND Sponsor (Safety Project Manager IND Office) according to 21 CFR 312.32.

It is the responsibility of the PI and the research team to ensure serious adverse events are reported according to the Code of Federal Regulations, Good Clinical Practices, the protocol guidelines, the sponsor's guidelines, and Institutional Review Board policy.

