9.3 Cardiac Toxicity Monitoring

As anthracyclines are known to have an adverse effect on cardiac function, each patient's cardiac function will be monitored through the Treatment and Follow-up Phases. Any left ventricular ejection fraction below 50% will be recorded as adverse events. If the left ventricular ejection fraction is reduced >10% to below 50% from the baseline assessment at the last Treatment Phase measurement, left ventricular ejection fraction will continue to be monitored every 3 months until a return to baseline or 1 year, whichever comes first.

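### DLTs count to Day 60, but new non-serious adverse events are recorded only to Day 35 after a single full induction, and no rule scores a dosed patient whose DLT status is unknown

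*Combined protocol and SAP*

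**What the plan says.** **DLT window.** Section 4.0 counts death in the first 60 days, and drug-related toxicity "occurring during the first 60 days from the start of study therapy (i.e., during the first cycle of therapy"). Sections 4.0 and 10.0 use this count for the acceptance rule (fewer than 5 DLTs in 15 patients) and for the stopping looks in Tables 8, 11 and 12.

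**Recording window.** Section 9.2.1 has adverse events entered from the first infusion "until 30 days after the last dose of study drug, with the exception of serious adverse events".

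**What follows it.**
- The end-of-treatment schedule (6.3) says: "Assess Adverse events that were ongoing at the time of discontinuation and record and report any new serious adverse events". Its limit for the latter is 30 days from discontinuation.
- Section 4.8 says: "Follow-up for CR duration, EFS and safety (if applicable) terminates at the time of relapse, start of salvage or non-protocol treatment for leukemia".
- The long-term schedule (6.4, opening "The following evaluations are completed during the follow-up phase") and Appendix 2 have no adverse-event row.
- The on-treatment schedule (6.2) says: "continually assess during Treatment Period and record and report any new serious adverse events (up to 30 days after completion of Treatment Period"). The documents do not define the Treatment Period in days.

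**Other routes.** Section 9.2.2 says "any serious adverse events that occur after the 30 day time period that are related to the study treatment must be reported". Section 9.3 says "Any left ventricular ejection fraction below 50% will be recorded as adverse events". Hematologic DLT has its own examination at Day 56 or later (4.0), and survival is followed to death (6.4).

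**Unknown DLT status.** Section 4.4 recruits an additional patient when one is discontinued for progressive disease or unrelated illness before DLT can be ruled out. Its purpose is to have enough patients evaluable for safety. Section 9.1 and the statistical methods in 10.0 make every dosed patient evaluable for safety or toxicity.

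**The concern.** The endpoint can outlast the data collection that feeds it. Section 9.2.1 itself explains that severe and serious are different things. The DLT definition rests on grade, while the only open-ended reporting route (9.2.2) rests on seriousness. An event can therefore qualify as a DLT by grade, not be serious, and arise after recording has stopped. Any such loss lowers the DLT count and never raises it, so an arm would look safer than it is.

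The second issue is how a dosed patient with incomplete observation enters the count. Section 10.0 has a rule for efficacy (lost to follow-up in the first two cycles is a failure) but none for DLT. Kept in the denominator as a non-DLT, such a patient dilutes the rate. Scored as a DLT, the same patient can stop an arm.

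**Working it through.** **1. Recording window against Day 60.** Inputs: doses on Days 1, 3 and 5 of the first induction (4.0); second induction on its Days 1 and 3, started on Day 28 or as early as Day 21 (4.5); recording to 30 days after the last dose (9.2.1).

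| Patient | Last dose | Recording ends | Days short of Day 60 |
|---|---|---|---|
| One full induction, no later dose | Day 5 | 5 + 30 = Day 35 | 25 |
| Day 1 dose only | Day 1 | 1 + 30 = Day 31 | 29 |
| Second induction from Day 21 | Day 23 | 23 + 30 = Day 53 | 7 |
| Second induction from Day 28 | Day 30 | 30 + 30 = Day 60 | 0 |

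Consolidation also moves the last dose and extends recording.

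**2. What can fall into the gap.** Section 4.0 counts the listed non-hematologic toxicities only under stated conditions: related grade 4 liver toxicity that does not resolve to grade 2 within 7 days, a related grade 3 or higher ejection-fraction fall, related grade 3 or higher creatinine elevation, and other related grade 3 or higher events that the principal investigator considers out of line with standard chemotherapy. Take away the routes listed above. What remains is new, related, non-serious events on that list. An example is a grade 3 creatinine elevation after Day 42, when scheduled biochemistry ends (6.2).

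**3. Effect of one lost DLT on acceptance.** 5/15 = 33.3% fails; 4/15 = 26.7% is acceptable.

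The documents give no loss rate, so the following is illustration only. Assume a share m of all DLTs goes unrecorded, ignore early stopping, and compute P(X ≤ 4) for X ~ Bin(15, p(1 − m)).

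| True DLT rate p | m = 0 | m = 10% | m = 20% | m = 30% |
|---|---|---|---|---|
| 0.33 | 0.415 | 0.526 | 0.639 | 0.747 |
| 0.40 | 0.217 | 0.322 | 0.448 | 0.585 |
| 0.50 | 0.059 | 0.120 | 0.217 | 0.352 |

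**4. Reproducing the plan's boundaries.** Prior beta(0.66, 1.34); posterior after x DLTs in n is beta(0.66 + x, 1.34 + n − x); stop if Pr(T_E > 0.33 | data) exceeds the cut. At cut 0.85 the smallest stopping counts are 4 of 5, 6 of 10, 8 of 15 and 10 of 20. At cut 0.95 they are 4, 7, 9, 11, 13, 15, 17 and 19 at n = 5 to 40 in steps of 5. Both sets match Tables 8, 11 and 12.

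**5. One patient with unknown status at a printed look.**

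| Look | Cut | Scored as non-DLT | Scored as DLT |
|---|---|---|---|
| n = 5 | 0.85 | 3/5: 0.847, continue | 4/5: 0.967, stop |
| n = 10 | 0.85 | 5/10: 0.837, continue | 6/10: 0.944, stop |
| n = 10 (Table 12) | 0.95 | 6/10: 0.944, continue | 7/10: 0.986, stop |
| n = 20 (Table 12) | 0.95 | 10/20: 0.930, continue | 11/20: 0.972, stop |

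The n = 20 row uses the same formula. It matters because section 4.0 reports that 100 units/m² was found safe and adds 25 patients there, so the later looks of Table 12 are the ones still to come at that dose.

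**The case against.** The strongest reply is that very little can be lost. An unrecorded DLT must be late, related, on the conditional list and judged non-serious. Several listed events could well be reported as important medical events under 9.2.2, and related serious events stay reportable after 30 days. Day 35 applies only to patients who get no further study drug. Patients whose response is undeclared stay on weekly evaluations (Appendix 1, note 3) and arguably within the Treatment Period of 6.2. The department guidelines for adverse-event recording, named in 9.2.1, are not in the documents and may go further. Most of this stands, and it is why the gap is called narrow. It does not close the gap, because 9.2.1 sets an explicit end and no passage in the documents overrides it for non-serious events.

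It is also fair that looks already passed cannot be given a scoring rule in advance. The remaining looks and the final rate can.

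Three stronger readings are tempting but unsupported.
- A reader might see two conflicting acceptance rules in section 4.0, fewer than 5 in 15 and below 33%. Read as a rate, 5/15 allows the same maximum DLT count as 33% at every n up to 99. They first differ at n = 100 (33 against 32), far above any arm size here.
- A reader might see two look units, since 10.0 speaks of subjects treated and Table 12 of patients evaluated. If every dosed patient is evaluable, these need not differ.
- A reader might infer that replacement lets an observed DLT be dropped. No passage allows that. The gap concerns only patients whose status is unknown.

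**Conclusion.** The mismatch is real and should be corrected. As written, up to 25 of the 60 DLT days lack routine recording of new non-serious events after one full induction with no later dose, 29 days after a Day 1 dose only, and 0 to 7 days after a second induction started on Day 28 or Day 21. The error can run in one direction only, and one event is enough to move an arm from 5/15 to 4/15. It would go too far to conclude that the DLT rate is materially biased: the documents give neither the number of patients who stop after one induction nor the frequency of late non-serious DLTs, and the loss shares tabulated above are assumptions.

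The scoring gap is secondary. Section 4.4 implies that a replaced patient was not evaluable, sections 9.1 and 10.0 say that the patient is, and at a look one DLT below the boundary the choice decides between continuing and stopping.

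Section 4.0 also equates the 60 days with the first cycle while defining a cycle as 28 days. That is editorial, since 60 days is stated explicitly.

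The conclusion assumes that 9.2.1 governs recording and that the department guidelines do not extend it.

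**What to change.** 1. Record adverse events that could meet the DLT definition until the later of Day 60 from first dose or 30 days after the last dose, including after relapse or the start of salvage. Bring 4.8, 6.2, 6.3 and 9.2.1 into line, define the Treatment Period, and add an adverse-event row to 6.4 and Appendix 2.
2. Reconcile 4.4 with 9.1 and 10.0. Keep all dosed patients in the toxicity set, and count every observed DLT, including any death by Day 60. State which scoring of unknown status the remaining looks and the final rate use. Report the rate with such patients scored as non-DLT and again as DLT.
3. Remove the reference to the first cycle from the 60-day definition.

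Cost: a short amendment, up to 25 to 29 more days of limited recording for patients who stop after one induction or part of one, and possibly a less favorable DLT rate. The stopping boundaries do not change.
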